5.4.2 Laboratory Assessments for Myeloma

All serum and urine lab tests must be sent to the central lab, except serum calcium and albumin which are performed locally, until disease progression or withdrawal of consent, even if the subject is discontinued from study therapy and has started new myeloma therapy.

Subjects without measureable urine M protein (< 200 mg/24 hours) at baseline and at the next two consecutive assessments do not have to submit q4 week urine samples with each cycle (but must submit q12 week urine samples) until SPEP M protein becomes undetectable. Therefore, at the time SPEP becomes undetectable, 24-hr UPEP collection should promptly resume and continue q4 weeks until SPEP becomes detectable.

Assessment of UPEP M protein and urine immunofixation at the time of possible CR/sCR is mandatory for all subjects, that is negative urine immunofixation for a minimum of 6 weeks is required to fulfill CR/sCR criteria, even in subjects with nonmeasurable values at baseline. Any local serum and urine myeloma lab tests that may also have been performed must also be reported in the CRF as requested by Sponsor to properly assess efficacy by protocol criteria.

- 1) **Serum:** serum protein electrophoresis (SPEP) for M protein quantification, total serum protein, immunofixation, and quantitative immunoglobulin assay.
 - a) Immunofixation of serum is required at baseline and to confirm CR regardless of whether measurable M-protein was present at baseline.
 - b) All other serum tests will be followed at each tumor assessment. Confirmation of \geq PR is required at least 6 weeks later.

- 2) **Urine:** 24-hour urine collection electrophoresis for M protein quantification, urinary light chains, and immunofixation. 24-hour urine must be collected with each cycle for all subjects, except for those subjects with no measurable M protein in the urine at baseline and at next two consecutive assessments.
- a) Immunofixation of urine is required at baseline and to confirm CR regardless of whether measurable M-protein was present at baseline.
 - b) All other urine tests will be followed at each tumor assessment. Confirmation of \geq PR is required at least 6 weeks later.

3) **Bone marrow aspiration/biopsy:**

Bone marrow sample	Local Laboratory	Central Laboratory
Aspirate ^a	
1) Samples required at the following times to evaluate percentage plasma cells:
 
 g) Screening (within 28 days of randomization) h) When subject is immunofixation negative in both serum and urine (second bone marrow sample not required for confirmation) for a minimum of 6 weeks 
In addition, evaluate flow cytometry to assess plasma cell clonality (ie, lambda and kappa IHC or flow cytometry to assess light chain restriction).
 
 a) At time of suspected disease progression, if needed (see Section 5.4.5.5) to assess progression in subjects who's myeloma become nonsecretory 	
1) Screening (within 28 days of randomization)
 
 a) send for genetic assessments (karyotype and FISH)^b
Biopsy	Not required by protocol unless an aspirate sample (at any time point above) is not available due to a dry tap or due to laboratory preferences of the local pathologist. IHC of biopsy for clonality by local lab if aspirate is not available.	

^a Should be replaced by core biopsy sample only if: 1) aspirate is not available at any time point due to a dry tap or 2) subject is immunofixation negative in serum and urine and flow cytometry is not available at the site.

^b Genetic assessments (karyotype and FISH) should be performed by the central laboratory on a fresh bone marrow sample. However, if a new bone marrow sample collection is not feasible and if this assessment was performed locally within the 28 days prior to randomization, the local results must be entered into the eCRF.

- 4) **Serum free light chain:** Serum should be collected at baseline and time of serum and urine IFE negativity for a minimum of 6 weeks to confirm CR and be sent to the central lab for serum free light chain analysis. Two values at least 6 weeks apart should be provided. The measurement of sFLC is required to document sCR using [Section 5.4.5](#), but is not a criteria for determining disease progression (see [Sections 5.4.1](#) and [5.4.5.5](#)).

- 5) Serum Corrected Calcium: Serum corrected calcium should be collected with each cycle for all subjects until disease progression.

5.4.3 Imaging Assessments for Myeloma

5.4.3.1 Skeletal Survey

Skeletal survey, by conventional radiography, for metastatic disease will be performed at screening (within 28 days prior of randomization), and on study if clinically indicated (development of compression fracture does not exclude response). Use of conventional or low dose CT scan (ie, of the spine) or MRI bone survey is acceptable. If imaging is performed on treatment for assessment of progression, the site must use the same modality of imaging as used in screening. The number and location of skeletal lesions and whether they are lytic should be recorded on the eCRF. On treatment survey should record whether there is an increase in the number or size of lytic lesions.

5.4.3.2 Assessment of Extramedullary Plasmacytoma

CT or MRI should be performed in all subjects if clinically indicated at baseline to assess for the presence of extramedullary plasmacytoma. To minimize unnecessary radiation in myeloma subjects where progression is primarily based on serum and urine M-protein, on study assessments should only be performed if clinically indicated (ie, pain, concern for disease progression), whether or not present at baseline, and at the time of CR/sCR assessment.

A sum of the products of the longest diameters and longest perpendicular diameter for all measurable lesions will be calculated at baseline. This sum will be used as the reference for on-study assessments by which to characterize the objective tumor response.

All tumor measurements must be made in millimeters. All documented measurable lesions are to be followed throughout the trial. All assessments to be used for tumor response evaluation, including the baseline assessment, must be performed using the same method for repeat assessment. CT and MRI scanning are the preferable methods of assessment. Conventional CT and MRI should be performed with contiguous cuts of 10 mm or less or with cuts of 5 (or 10) mm if spiral CT scanning is used. Imaging-based evaluation is preferred to evaluation by clinical examination. Evaluation by chest x-ray is less preferable than CT or MRI, and should only be used for well-defined lesions surrounded by aerated lung. Clinical examination is only acceptable when lesions are superficial, such as a skin nodule or palpable lymph node. Skin lesions must be documented by a photograph with a ruler. Ultrasound is not acceptable for documentation of measurable disease.

Duplicate copies of all imaging studies used for tumor response evaluation will be made available for review by the Sponsor upon request.

Measurable disease are lesions that can be accurately measured in 2 dimensions and both diameters must be ≥ 20 mm when evaluated by standard CT scanning or ≥ 10 mm when evaluated by spiral CT scanning. The minimum diameter size should be at least twice the slice thickness.

Non-measurable disease are all other lesions (or sites of disease), including those that are too small (ie, do not meet above criteria), occur within a previously irradiated area (unless they are documented as new lesions since the completion of radiation therapy), bone lesions, leptomeningeal disease, ascites, pleural or pericardial effusion (exception for effusions documented by cytology as not malignant or present at baseline without progression), lymphangitis cutis/pulmonis, abdominal masses that are not pathologically/cytologically confirmed and followed by imaging techniques, and cystic lesions.

5.4.4 Independent Review Committee

The following information will be submitted to an Independent Review Committee (IRC) for final assessment of objective response based on:

1. The subject's laboratory results (electronically and via CRF)
2. All imaging results via CRF
3. Local pathology results via CRF
4. Local pathology results of bone marrow samples for confirmation of stringent CR.

The criteria for IRC review are defined in a separate IRC charter.

5.4.5 Definitions of Response

5.4.5.1 Complete Response (CR)/stringent CR (sCR)

A CR requires that all of the following criteria be achieved:

1. Negative immunofixation ("IF") on both serum and urine, maintained for a minimum of 6 weeks and
2. A bone marrow aspirate or biopsy containing < 5% plasma cells. It is not essential to perform a trephine biopsy, but if a biopsy is performed this must also contain < 5% plasma cells (although not required for documentation of CR using the EBMT criteria, light chain restriction (flow or IHC for kappa and lambda light chain in the bone marrow should also be assessed to assist in classification of stringent CR using the IMWG criteria)¹⁷ and
3. If skeletal survey showed osteolytic bone lesions, there should be no increase in the size or number (development of a compression fracture does not exclude response) and
4. If screening scans showed extramedullary plasmacytomas, complete disappearance of any must be noted.
5. For assessment of stringent CR, per IMWG criteria, all criteria for CR must be upheld. In addition, bone marrow sample must be assessed for light chain restriction (as mentioned in bullet 2 above) and serum free light chains must be normalized at two time points at least 6 weeks apart, at the time of CR assessment.

5.4.5.2 Partial Response (PR)

Subjects in whom some, but not all, the criteria for CR are fulfilled are classified as PR, providing the remaining criteria satisfy the requirements for PR. This includes subjects in whom routine electrophoresis is negative but in whom IF has not been performed.

1. Greater than or equal to 50% reduction in serum M-protein, maintained for a minimum of 6 weeks.
2. Reduction of $\geq 90\%$ in urinary light chain excretion or a decrease to < 200 mg/ 24 hours, maintained for a minimum of 6 weeks.
3. Greater than or equal to 50% reduction in the size of extramedullary plasmacytomas present at baseline (by radiography or clinical examination using bidimensional measurements).
4. If a skeletal survey is performed, no increase in the size or number of lytic lesions (development of a compression fracture does not exclude response).

5.4.5.3 Very Good Partial Response (VGPR)

VGPR, a subset of PR, is not formally included in the EBMT criteria but is derived from the IMWG criteria.¹⁷ Because VGPR is commonly used to measure depth of response in MM, this response must be reported by investigator and IRC and is defined by:

1. Serum and Urine M-protein detectable by immunofixation but not on electrophoresis and that is confirmed in a subsequent assessment OR
2. 90% or greater reduction in serum M-protein plus urine M-protein level < 100 mg per 24 h and that is confirmed in a subsequent assessment.

5.4.5.4 Minor (Minimal) Response (MR)

Subjects who have reduction in M-protein or plasmacytoma but do not meet the criteria for PR are classified as MR if they meet all the following definition:

1. Between 25 - 49% reduction in serum M-protein, maintained for a minimum of 6 weeks.
2. Between 50 - 89% reduction in urinary light chain excretion which still exceeds 200 mg/24 hours, maintained for a minimum of 6 weeks.
3. Between 25 - 49% reduction in the size of extramedullary plasmacytomas.
4. If a skeletal survey is performed, no increase in the size or number of lytic lesions (development of a compression fracture does not exclude response).

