5.4.5.6 Stable Disease/No Change

Does not meet criteria for any of the categories above.

[REDACTED]

[REDACTED]

[REDACTED]

[REDACTED]	[REDACTED]	[REDACTED]	[REDACTED]	[REDACTED]
[REDACTED]	[REDACTED]	[REDACTED]	[REDACTED]	[REDACTED]
		[REDACTED]	[REDACTED]	
		[REDACTED]	[REDACTED]	
	[REDACTED]	[REDACTED]	[REDACTED]	
		[REDACTED]	[REDACTED]	
	[REDACTED]	[REDACTED]	[REDACTED]	
		[REDACTED]	[REDACTED]	
	[REDACTED]	[REDACTED]	[REDACTED]	
		[REDACTED]	[REDACTED]	
[REDACTED]	[REDACTED]	[REDACTED]	[REDACTED]	[REDACTED]
		[REDACTED]	[REDACTED]	
	[REDACTED]	[REDACTED]	[REDACTED]	
		[REDACTED]	[REDACTED]	
[REDACTED]	[REDACTED]	[REDACTED]	[REDACTED]	[REDACTED]
		[REDACTED]	[REDACTED]	
	[REDACTED]	[REDACTED]	[REDACTED]	
[REDACTED]	[REDACTED]	[REDACTED]	[REDACTED]	[REDACTED]
[REDACTED]	[REDACTED]	[REDACTED]	[REDACTED]	[REDACTED]
[REDACTED]	[REDACTED]	[REDACTED]	[REDACTED]	[REDACTED]
[REDACTED]	[REDACTED]	[REDACTED]	[REDACTED]	[REDACTED]
[REDACTED]	[REDACTED]	[REDACTED]	[REDACTED]	[REDACTED]
[REDACTED]	[REDACTED]	[REDACTED]	[REDACTED]	[REDACTED]
[REDACTED]	[REDACTED]	[REDACTED]	[REDACTED]	[REDACTED]

[REDACTED]		[REDACTED]		
[REDACTED]	[REDACTED]	[REDACTED]	[REDACTED]	[REDACTED]
[REDACTED]	[REDACTED]	[REDACTED]	[REDACTED]	[REDACTED]
[REDACTED]	[REDACTED]	[REDACTED]	[REDACTED]	[REDACTED]
[REDACTED]	[REDACTED]	[REDACTED]	[REDACTED]	[REDACTED]
[REDACTED]	[REDACTED]	[REDACTED]	[REDACTED]	[REDACTED]

[REDACTED]

[REDACTED]

[REDACTED]

[REDACTED]

[REDACTED]

[REDACTED]

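### Protocol 5.4.5.4 caps minor response (MR) on every marker and has no carry-down from PR, so a subject with one marker at PR level and another only at MR level falls to stable disease

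*Protocol*

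**What the plan says.** Protocol 5.4.5.4 opens with "Subjects who have reduction in M-protein or plasmacytoma but do not meet the criteria for PR" and says they are "classified as MR if they meet all the following definition". The three measured items are:

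- serum: "Between 25 - 49% reduction in serum M-protein, maintained for a minimum of 6 weeks";
- urine: "Between 50 - 89% reduction in urinary light chain excretion which still exceeds 200 mg/24 hours", also held for 6 weeks;
- plasmacytoma: "Between 25 - 49% reduction in the size of extramedullary plasmacytomas".

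Each has an upper limit, and nothing in the section admits a better value.

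Protocol 5.4.5.2 treats the step from CR to PR differently. Its opening clause applies where "some, but not all, the criteria for CR are fulfilled are classified as PR". That carry-down is subject to one condition, which reads "providing the remaining criteria satisfy the requirements for PR". The PR thresholds have no upper limit: serum reduction of at least 50%, urine reduction of at least 90% or a fall below 200 mg/24 h, and plasmacytoma reduction of at least 50% where one was present at baseline.

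Stable disease in 5.4.5.6 is the residual category: "Does not meet criteria for any of the categories above".

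SAP 7.5.5 tabulates MR and SD as separate categories of best overall response by arm, for the IRC and for the investigator. It then gives two concordance measures, one on the exact category and one on responder versus non-responder.

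**The concern.** A response scale should be ordered: improving one marker while the others stay the same should never lower the category. Upper limits on every MR item, combined with a requirement to meet all of them, break that order when one marker has passed the MR range and another has not reached PR. The subject is then too good for MR on one marker, not good enough for PR on the other, and drops into the residual category.

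At stake are the split between MR and SD in the best overall response tables and the agreement measure built on exact categories. There is also a consistency risk. Investigators work from the protocol, while Protocol 5.4.4 places the IRC's rules in a separate charter. If the charter handles mixed responses and the protocol does not, the two assessors apply different rules and exact-category agreement suffers for that reason alone.

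**Working it through.** The documents state no figure to reproduce; this is a check of the classification rules. I applied the text of 5.4.5.2, 5.4.5.4 and 5.4.5.6 literally to worked cases.

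Inputs from the protocol:

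- PR: serum ≥ 50%, and urine ≥ 90% or < 200 mg/24 h (plus plasmacytoma ≥ 50% if present). All applicable items are taken as required.
- MR: serum 25–49%, and urine 50–89% with more than 200 mg/24 h left (plus plasmacytoma 25–49% if present). All are required.
- SD: neither of these, and no progression.

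Assumptions: baseline urine 1000 mg/24 h, because the documents give no distribution; every value held for 6 weeks; no plasmacytoma unless stated. Urine left = 1000 × (1 − reduction), so 60% leaves 400, 79% leaves 210 and 95% leaves 50 mg/24 h.

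| Case | Serum | Urine (left) | PR? | MR? | As written | With carry-down |
|---|---|---|---|---|---|---|
| A | −30% | −60% (400) | no: both short | yes | MR | MR |
| B | −60% | −60% (400) | no: urine | no: serum 60 > 49 | SD | MR |
| C | −30% | −95% (50) | no: serum | no: urine 95 > 89, and 50 is not above 200 | SD | MR |
| D | −49% | −79% (210) | no: both short | yes | MR | MR |
| E | −50% | −79% (210) | no: urine | no: serum 50 > 49 | SD | MR |
| F | −60% | −95% (50) | yes | – | PR | PR |

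B equals A on urine and is better on serum, yet ranks below A. E differs from D by one percentage point of serum improvement and drops a category. Plasmacytoma behaves the same way. With serum −30% and urine −60%, a 30% plasmacytoma reduction gives MR and a 60% reduction gives SD.

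F marks the boundary of the problem: once every followed marker reaches PR level, the subject is PR. The inversion needs at least two followed markers, one at PR level and another only within the MR range. A subject with one marker at PR level and another short of the MR minimum is SD with or without the carry-down.

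Next, which analyses use the MR/SD split:

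- ORR counts PR or better (Protocol 8.3.2, SAP 4.1.2), so MR and SD are both non-responders. No change.
- Progression is judged against the nadir (Protocol 5.4.5.5), and PFS is built on progression and death. No change.
- OS does not use response. No change.
- Responder/non-responder concordance (SAP 7.5.5): no change.
- MR and SD rows of the best overall response tables, and exact-category concordance (SAP 7.5.5): these change.

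**The case against.** **MR is evidently meant as the fallback below PR.** The opening of 5.4.5.4 describes subjects with some reduction who miss PR, and a sensible assessor would read the ranges as minimums. That is probably the intent, but the text asks for every item within a closed range, and no other section supplied corrects it.

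**Best response is taken over time.** This stands and narrows the point. Best overall response uses all on-study data (Protocol 8.3.2, SAP 4.1.2), with assessments every 4 weeks. A subject who held the MR ranges for 6 weeks before reaching a mixed pattern keeps MR, and one who later reaches PR is PR.

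**The IRC charter may already contain a mixed-response rule.** This also stands. The charter was not supplied, so the effect on the IRC column cannot be settled from these documents.

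Two stronger readings are tempting, and the documents do not support either:

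- A reader might infer that anyone who beats the MR range on one marker becomes SD. A subject followed on serum alone with a 60% fall is PR.
- A reader might infer that subjects with serum-only disease can never be MR, because they cannot meet the urine and plasmacytoma items. That applies items to disease the subject does not have. The opening of 5.4.5.4 joins M-protein and plasmacytoma with *or*, PR item 3 is limited to plasmacytomas present at baseline, and SAP 4.1.1.1 requires serum and urine results only where measurable at baseline. The MR items do omit such a qualifier, which justifies a clarifying phrase. It does not justify counting every serum-only MR as lost.

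**Conclusion.** The MR rule is wrong as written, and the error is minor. It mis-orders subjects with two or more followed markers whose best confirmed state has one marker at PR level and another only at MR level. Their number cannot be derived: the documents give neither the share of subjects followed on two markers nor the frequency of mixed responses, and any head count would rest on assumption alone.

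The consequences are confined to the MR and SD rows of the best overall response tables and to exact-category concordance. The same protocol rule serves both arms and the IRC is blinded to treatment (SAP 2.3), so nothing here indicates a bias between arms.

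This rests on two conditions. First, the PR list is read as requiring every applicable item. Section 5.4.5.2 implies this but does not print *all* over the list. If one PR item sufficed, case B would be PR, and the question would reach ORR, which gates the OS test under SAP 7.5.11. Second, the IRC charter contains no rule that already resolves mixed responses; if it does, the IRC column is already right and only the protocol text and the investigator column need correcting. Some sections of both documents are blacked out, so the list of affected analyses covers the visible text only.

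**What to change.** 1. In 5.4.5.4, add a carry-down clause parallel to the one in 5.4.5.2: a subject who meets some but not all PR criteria is MR if the remaining criteria satisfy at least MR.
2. In both 5.4.5.2 and 5.4.5.4, state that all applicable items are required, and that the urine and plasmacytoma items apply only where that disease was measurable or present at baseline. SAP 4.1.1.1 and PR item 3 already contain suitable wording. This also settles the reading of the PR list on which ORR depends.
3. Check the IRC charter for a mixed-response rule and align it with the same text, so that IRC and investigator categories are compared under one definition.

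The cost is small. No new visits or data are needed, and alpha, sample size and event counts are untouched. Some subjects move from SD to MR, and the categories can be re-derived from stored laboratory and imaging data. Investigator categories need the same re-derivation if concordance is to compare like with like. The change is best made before the study team has access to the randomization codes.

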5.4.5.5 Progression of Disease (PD)

Progression

Progression describes a definite increase in disease activity relative to the nadir in 2 consecutive assessments in subjects not in CR, whereas the term “relapse from CR” applies to a recurrence of evident disease in subjects previously in CR. The date of EBMT based disease progression is the first date of two consecutive values fulfilling the criteria for disease progression.

Any of the following list is sufficient for PD:

1. Increase of > 25% in serum M-protein (also an absolute increase of at least 5 g/L) and confirmed by at least 1 investigation.
2. Increase of > 25% urinary light chain excretion (which must also be an absolute increase of at least 200 mg/24-hours and confirmed by at least 1 investigation).
3. Increase of > 25% plasma cell percentage in the marrow (which must also be an absolute increase of at least 10%).
4. Definite increase in the size or number of lytic bone lesions or extramedullary plasmacytomas (development of a compression fracture does not exclude continued response and may not indicate progression).
5. Development of hypercalcemia (corrected serum calcium greater than 11.5 mg/dL; 2.8 mmol/L) not attributable to any other cause.

Relapse from CR (for subjects in CR)

Subjects who have documented CR and then achieve at least one of the following criteria are classified as relapse from CR. According to the EBMT criteria, relapse from CR is considered to be progression of disease. The date of EBMT based relapse from CR is the first date of two consecutive values fulfilling the criteria for relapse.

1. Reappearance of serum or urinary M-protein on immunofixation or routine electrophoresis, confirmed by at least one further investigation and excluding oligoclonal reconstitution.
2. Greater than or equal to 5% plasma cells in a bone marrow aspirate or on trephine bone biopsy.
3. Any of the definitions met for Progression.

